### **Marijuana Administration at Home.**

Unlike other studies done in the United States to date, the proposed work will utilize a design that is observational but contains some experimental elements. Specifically, at the end of Appointment 1 (Baseline/Session 1) participants will be given instructions to purchase 3 grams of either a normally high THC strain, a medium THC strain, or a low THC strain at a dispensary (The Farm) in Boulder, Colorado. The normally high THC smoked flower strain contains 18% THC and 0% CBD and edibles can range from a low of 2.5 mg to greater than 10 mg of THC and 0 mg of CBD. **Please note the term “high” is relative given that the average potency in Colorado exceeds 18% and edibles are normally packaged in 10 mg THC doses.** The medium flower strain contains 12% THC and 0% CBD. The low flower THC strain contains 6% THC and 0% CBD. Colorado requires all strains of flower and edibles to be tested by a state licensed lab, which allows us to have a precise measure of potency to operationalize our high, medium, and low THC strains. Furthermore, the dispensary that we will work with (The Farm - see letter of support) performs cannabinoid and terpene potency testing on each batch produced. The dispensary will set aside a specific lot of the strains which will be labeled as “Strain A”, “Strain B”, and “Strain C” such that participants, dispensary staff, and research staff will be blind to which strain was purchased. Thus, 3 grams of each marijuana strain will be packaged in childproof bottles labeled as “Strain A”, “Strain B”, and “Strain C.” Our preliminary data suggests that 3 grams is sufficient for the study. [name] (co-investigator) will maintain the blind. The instruction to purchase “A” or

“B” or “C” will be urn randomized across participants such that equal numbers of male and female participants are included in the high, medium, and low conditions. The observational aspect of the design involves the instruction that participants can use as little or as much of the marijuana as they wish during the five days prior to the experimental appointment. The five-day period allows each participant to become accustomed to the strain. Subjects are prompted by email or text message to report how much was used each day using an online reporting system. On the fifth day, the research assistant calls the participant one hour prior to their appointment to remind the participant about the upcoming appointment from the research team.

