### **Analysis Plan for Hypotheses 1 and 2**

Analyses will be conducted primarily on the SAS system for Windows Version 9.1, which includes capabilities to test multilevel models that include nonlinear effects and missing data (Cohen et al., 2013). Preliminary analyses will include checking the data for normality and reliability. To test the success of random assignment, the equivalence of conditions across all pretest measures will be assessed via t-tests on continuous items (e.g., depressive symptoms) and  $\chi^2$  tests of categorical items (e.g., race). We will use the Bonferroni approach (Keppel, 1991) to correct for alpha inflation with a familywise alpha of .05. Tests of the main hypotheses for effects of THC on primary outcomes will be conducted in a multilevel framework to account for the repeated observations within participants over time. Random coefficient regression (RCR; Cohen et al., 2013) models in SAS Proc Mixed will be utilized for continuous outcomes (e.g., working memory, drug reward).

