### **Effects of THC Potency on THC Blood Levels, Working Memory, and Reward**

The first aim is designed to test whether the “potency” of marijuana in terms of THC level in the plant translates directly to THC levels in the blood. To test **Hypothesis 1**, those individuals who receive the high THC strain will demonstrate significantly greater blood THC levels, we will utilize random coefficient regression (RCR; Cohen et al., 2013) via SAS Proc Mixed. The between subjects factor will be strain (high THC versus medium THC versus low THC) and the within subjects factor is time (Time 1, Time 2, Time 3, Time 4). Blood level of THC is the dependent measure. The test of the strain X time interaction will indicate whether the pattern of effects is such that blood levels increase to a greater degree and remain higher across the course of the study in the strains with higher THC. Thus, we expect both a significant interaction as well as a main effect of strain. Assuming a significant omnibus test of the interaction, we will decompose the interaction

via planned posthoc contrasts in order to understand at which time points the three strains are different. At Appointment 1, Time 1 (baseline) we do not expect differences in THC since none of the participants will have switched strains. Appointment 2, Time 2 is the sober, before use at Time 3. Thereafter, we expect a difference in THC at Appointment 2, Time 3 in the high THC versus the medium and low THC groups, and that while all groups will decrease in THC over the course of the laboratory appointment between Time 3 and 4, the high THC group will continue to show higher blood levels than the medium THC group, and the medium THC group will show higher blood levels than the low THC group. Note that we will include a quadratic effect in the multilevel model both to appropriately model the quadratic effect and whether that quadratic trend differs by condition. It is important to note that since we are not directly controlling administration, and have instructed participants to ingest the marijuana ad libitum, that they themselves may moderate their consumption to achieve “desired” THC levels, as our pilot data suggest. Thus, those in the low and medium THC group may ingest more in order to match their typically desired level, and thus the groups might converge. In this case, it is possible that we may see fewer difference in blood levels of THC, or non-significant differences at some timepoints across groups.

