**Hypothesis 2** tests whether blood levels of THC are positively associated with diminished working memory and greater rewarding effects of the marijuana, operationalized with the DEQ. If analyses of Hypothesis 1 show that there are main effects by group suggesting that the higher THC strain results in significantly higher THC levels in the blood than the medium or low THC strains, the between-groups variable for models testing Hypothesis 2 will be group and we will include all four time points. Since participants were randomly assigned to group, this test allows for the highest internal validity in terms of causal conclusions about the effects of THC. If, on the other hand, participants titrate their own use such that there are few reliable between-groups differences, then actual blood levels of THC will become the between-groups (continuous) independent variable in tests of Hypothesis 2 and we will utilize timepoints 3-4 as the within-subjects effect of time. Our preliminary studies confirm wide variability in THC levels even among individuals using the same strain, so there will be adequate between-participant variability for these analyses. In either case, we will again use the RCR approach described above, and standard approaches to the estimation of interactions in regression (Aiken & West, 1991) in the case of a continuous IV (i.e., mean-centering prior to creation of the interaction term). In each model, the predictors will include the group variable (or continuous THC blood levels), a time variable, and their interaction.

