Self-Rated Question of Diet Quality	
 
In general, how healthy is your overall diet? Would you say (1) excellent, (2) very good, (3) good, (4) fair, or (5) poor? (Loftfield, Yi, Immerwahr, Eisenhower)
 
	
Leisure-Time Categorical Item (L-Cat)	
 
A single item comprised of six descriptive categories ranging from inactive to very active (Kiernan, Schoffman, Lee, Brown, Fair, Perri, & Haskell, 2013). Each category consists of 1–2 sentences describing common activity patterns differing in frequency, intensity, duration, and types of activities, thus encompassing content validity (van Poppel, Chinapaw, Mokkink, van Mechelen, & Terwee, 2010).
 
	
Marijuana Consumption Questionnaire (MCQ)	
 
Ask participants to reflect on the frequency and quantity of their cannabis use, age of first use, and perceived availability of cannabis. (Heishman, Singleton, & Liguori, 2001)
 
	
Marijuana Dependence Scale (MDS)	
 
The MDS based on DSM V criteria that were converted to a self-report measure. Individuals respond 'yes' or 'no' to each dependence item (e.g., "When I smoked marijuana, I often smoked more or for longer periods of time than I intended"). The items are then summed to form the scale. This scale has been previously used in the cannabis literature. The internal consistency of the MDS (based on the DSM IV) was good in our pilot study (<math>\alpha = .73</math>) and even better in previously published reports (<math>\alpha = .85</math>; see Stephens, Roffman, & Curtin, 2000).
 
	
Alcohol Use Disorders Identification Test (AUDIT)	
 
The AUDIT (Babor et al., 2001) will be used to examine the extent of co-morbid alcohol use and problems related to alcohol use.
 
	
The Beck Depression Inventory-II (BD-II)	
 
Consists of 21 scaled statements designed to assess symptoms of depression and will be administered to examine comorbid depression and covary baseline differences if necessary. (Beck, Steer, Ball, & Ranieri, 1996)
 
	

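### If participants titrate, the blood-THC model for Hypothesis 2 names neither the pre-use working-memory score nor sex, so its association is open to confounding and less precise than it need be

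*Protocol*

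**What the plan says.** For Hypothesis 1 the protocol (Effects of THC Potency on THC Blood Levels, Working Memory, and Reward) states: "The between subjects factor will be strain (high THC versus medium THC versus low THC) and the within subjects factor is time". It adds a quadratic trend: "Note that we will include a quadratic effect in the multilevel model".

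Hypothesis 2 has two versions. If strain produces main effects on blood THC, strain is the predictor and all four times are used. If participants titrate so that the groups differ little, blood THC becomes a continuous predictor and "we will utilize timepoints 3-4 as the within-subjects effect of time". For both versions: "In each model, the predictors will include the group variable (or continuous THC blood levels), a time variable, and their interaction".

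Four other places bear on this.

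- Marijuana Administration at Home: assignment is "urn randomized across participants such that equal numbers of male and female participants are included in the high, medium, and low conditions".
- XII. Procedures, instrument table: the neurocognitive battery, including List Sorting Working Memory, is given at Sessions 1 to 4. The DEQ is given at Sessions 3 and 4 only. The Timeline Follow-Back covers the 30 days before baseline.
- Same table: the Beck Depression Inventory "will be administered to examine comorbid depression and covary baseline differences if necessary". The Beck Anxiety Inventory carries the same condition.
- Analysis Plan for Hypotheses 1 and 2: "To test the success of random assignment, the equivalence of conditions across all pretest measures will be assessed via t-tests on continuous items".

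**The concern.** The blood-THC model is not a remote fallback. The protocol says its pilot data suggest that people adjust consumption to reach a desired level, and that is the condition that brings this model in. Randomisation then no longer protects the comparison, because each participant chooses the exposure after assignment. The inclusion criteria require use at least 4 times a month and set no upper limit, so usual use can vary widely. If usual use or stable ability is related both to blood THC and to memory performance, a difference between people appears as a THC-memory association.

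The scores that would separate much of this are collected at Sessions 1 and 2. Restricting the model to Times 3 and 4 leaves them as neither outcome nor covariate. Sex is also absent from every stated model, although the design balances on it. Finally, adjusting when necessary, with no definition of necessary, leaves some covariates open to choice after the data are seen.

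**Working it through.** **Inputs.** ICC .6, N=99 (33 per group), 3 groups, 4 times, f=.12, two-sided alpha .05 (Power Analysis section). Retention 90% (The impact of attrition). All other inputs are marked as assumptions.

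**The plan's own figure.** For the within-between interaction, lambda = f² × N × m / (1 − ICC) = .0144 × 99 × 4 / .4 = 14.26 on 6 and 288 df, which gives power .811. For attrition, 33 / .9 = 36.7, so 37 per group and 111 in all. The stated sizes reproduce, and this point changes neither.

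**Precision in the working-memory blood-THC model.** Take unit variance and correlation .6 between any two sessions.

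- Variance of the Time 3-4 mean: (1 + .6) / 2 = .80.
- One pre-use score: covariance .6, so the share removed is .36 / (.80 × 1) = .45.
- Mean of two pre-use scores, itself with variance .80: .36 / (.80 × .80) = .5625. The SE ratio is √.4375 = .66. In simulation with THC unrelated to ability, the SE fell from .091 to .060.

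**Confounding.** Assume a true THC effect of zero and a correlation c between stable ability and blood THC. The protocol gives no value for c. Simulated rejection rates at N=99 (4000 runs), adjusting for the mean of two pre-use scores:

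| c | Unadjusted | Two pre-use scores |
|---|---|---|
| 0 | 4.6% | 4.9% |
| 0.1 | 14% | 7% |
| 0.2 | 40% | 10% |
| 0.3 | 75% | 17% |

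With one pre-use score the correlations are: THC with outcome, c√(.6/.8) = .866c; THC with the score, c√.6 = .775c; outcome with the score, √.45 = .671. The partial correlation is (.866c − .775c × .671) / √[(1 − .6c²) × .55], which is .047, .095 and .144 for c = 0.1, 0.2 and 0.3. Multiplying the Fisher transform by √95 gives z = .46, .92 and 1.41, so rejection rates are about 7%, 15% and 29%. Adjustment reduces the bias but does not remove it, because a pre-use score measures ability with error.

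**Sex in the blood-THC model.** Assume sex correlates r with both THC and outcome. The induced correlation is r². For r = .2 or .3 this is .04 or .09. Multiplying the Fisher transform by √96 gives z = .39 or .88, so type I error is about 7% or 14% without sex.

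**Sex in the strain models.** The variance of a four-time mean is .6 + .4/4 = .70. If sex explains 2%, 5% or 10% of total outcome variance (assumed range), the variance for the strain main effect falls by .02/.70 = 3%, .05/.70 = 7% or .10/.70 = 14%. The standard error of a strain × time contrast is 0.220 with and without a sex main effect.

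**The case against.** The strongest reply is that the stated list is not closed. The predictors are those the model will include, a quadratic term is added elsewhere, and a full covariate list often sits in a SAP, which is not at hand. This has some force. The absence of sex alone would be a minor matter. But limiting the blood-THC model to Times 3 and 4 is a positive choice, and it sets aside collected pre-use scores in the version where randomisation gives no protection.

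Second, the protocol ties causal conclusions to the randomised comparison and words Hypothesis 2 as an association. That stands. The confounding concerns the blood-THC version, not the randomised flower comparison, and its size rests on assumed correlations.

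Third, the .6 is a planning average across assessments, not a measured correlation between pre-use and intoxicated memory scores. That also stands, so the 45% and 56% are conditional on it.

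Several stronger readings are tempting but unsupported:

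- **Omitting sex weakens the powered test.** It does not. A time-constant sex effect leaves the strain × time contrast unchanged.
- **Sessions 1 and 2 are both sober baselines.** Only Session 2 is described as sober. No cannabis abstinence is stated for Session 1. Session 2 follows five days on the strain, so it is a pre-use score and not a baseline.
- **Baseline tests decide which covariates enter.** The protocol does not link the two. The conditional wording appears only for the depression and anxiety inventories. Baseline comparison also has a real purpose for edible users, whose groups form naturally.
- **Baseline adjustment would repair all of Hypothesis 2.** The DEQ has no pre-use score.

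**Conclusion.** The point holds for the blood-THC version of Hypothesis 2. As stated, that model compares people on a self-selected exposure without the pre-use working-memory score, usual use or sex, although all three are collected. Under ICC .6 and equal correlations, the unused precision is about 45% of the variance of the Time 3-4 mean with one pre-use score and 56% with two. The confounding cannot be sized from the protocol. An ability-THC correlation of only 0.1 would raise the error rate to about 14%, and 0.3 to about 75%. Two pre-use scores bring these to about 7% and 17%, and one score to about 7% and 29%.

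For sex in the strain models the gain is modest and confined to the strain main effect. That effect still matters, because it decides which version of Hypothesis 2 is run. The sample-size calculation and the powered interaction test are unaffected.

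**What to change.** 1. In the working-memory blood-THC model, pre-specify the Session 2 pre-use score, sex and Timeline Follow-Back use frequency. Session 1 may be added, and the calculation favours it, with a note that no cannabis abstinence is stated for that session.
2. In the DEQ blood-THC model, pre-specify sex and use frequency only.
3. Include sex in the strain models, on the ground that it helps the strain main effect.
4. Replace conditional adjustment for depression and anxiety scores with a list fixed in advance. Do not use baseline significance tests to select covariates. Baseline values can be reported descriptively.
5. Report the blood-THC result as an association, and say that residual confounding remains after adjustment.

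The cost is wording and a few degrees of freedom, since every variable is already collected. Adjusting for Session 2 also narrows the question: the estimate then concerns the acute effect after five days on the strain, not any change that built up over those days. The text should say so.

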## V. FUNDING

---

This study is funded by a grant from NIDA.

## VI. ABOUT THE SUBJECTS

---

Ethnic diversity of this sample is expected to be representative of the greater Boulder-Denver area at large. The researchers know this population has a common tendency to use either marijuana flowers or marijuana edibles, thus assigning them to the correct condition will not be difficult.

**Criteria for inclusion in the study are:**

1. Must be between the ages of 21 and 70 and provide informed consent;
2. Must have prior experience with edibles in order to be eligible to participate in the edible group;
3. Must have used marijuana at least 4x per month in the past month. This includes any form of marijuana consumption including flower, oil, wax, tinctures and edibles;

4. Must not report currently using a strain with greater than 1% CBD or less than 18% THC. This will ensure that there are no subjects who could be harmed by switching to a lower CBD/higher THC strain. All of the subjects in our preliminary study would have met this criterion.
5. Must not be a University of Colorado student or employee;
6. Must report not using other drugs (cocaine, opiates, methamphetamine) in the past 60 days or test positive on a urine test for those drugs of abuse at baseline;
7. Must not smoke greater than 5 cigarettes a day;
8. Must have a breath alcohol level of 0 at screening (to sign consent form) and must not report drinking greater than 3x per week and greater than 5 drinks on occasion for men and 4 drinks on occasion for women;
9. Female subjects must not be pregnant, as indicated by a pregnancy test which will be administered at baseline, or trying to become pregnant;
10. Must not donate plasma, blood, or platelets for 7 days prior to the 2 appointments and 7 days after;
11. Must not be in treatment for psychotic disorder, bipolar disorder or schizophrenia.

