### **Overview and Design of Study 1 (e.g., Aim 1, Hypotheses 1 and 2).**

Study 1 is designed to test the hypothesis that a high THC strain of marijuana will be associated with greater blood levels of THC and greater harmful effects, as compared to a lower THC strain, when used in a

naturalistic environment. To that end, regular flower marijuana users, who, according to our preliminary data, typically use marijuana with a THC potency of ~18%, will be assigned to use one of three strains with no CBD but with different THC potencies (low, medium, or high: e.g. 6%, 12%, or 18% THC for smoked flower) and regular edible marijuana users who typically purchase 10 mg products will be allowed to use as they normally would (producing naturally occurring low, medium, and high groups: e.g. less than 2.5mg to greater than 10 mg THC n=33 per group) for five days prior to participating in the experimental session. Measures will be collected at Appointment 1: (Baseline/**Session 1**), after 5 days of using the assigned strain, but in a sober condition before use in our mobile laboratory at Appointment 2: (**Session 2**), they will then return to their home to use the assigned strain and return to the mobile laboratory (**Session 3**), and 60 minutes after their last use at home (**Session 4**). Details regarding sample ascertainment, marijuana administration, timing of measures to be collected, power analyses, and the analytic plan for Study 1 follow. Thus, Study 1 will involve a 3 Cannabis strains: high, medium, and low THC x 4 (Time: 1, 2, 3, 4) mixed factorial design.

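### The design describes regular edible users, but the inclusion criteria admit anyone with prior edible experience to edible dose groups that are not randomised

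*Protocol*

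**What the plan says.** *Overview and Design of Study 1* defines two populations by the form they habitually use. The flower participants are "regular flower marijuana users, who, according to our preliminary data, typically use marijuana with a THC potency of ~18" per cent, and they are assigned to a strain. For edibles, "regular edible marijuana users who typically purchase 10 mg products will be allowed to use as they normally would". Dose groups then arise from what people choose: "producing naturally occurring low, medium, and high groups: e.g. less than 2.5mg to greater than 10 mg THC n=33 per group".

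*Criteria for inclusion in the study* sets a different bar. Item 2 reads "Must have prior experience with edibles in order to be eligible to participate in the edible group". Item 3 reads "Must have used marijuana at least 4x per month in the past month" and continues "This includes any form of marijuana consumption including flower, oil, wax, tinctures and edibles". Item 4 reads "Must not report currently using a strain with greater than 1% CBD or less than 18% THC". *Participant Recruitment and Selection* says the technician screens callers against these criteria.

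The opening paragraph of *About the Subjects* bears on placement: "The researchers know this population has a common tendency to use either marijuana flowers or marijuana edibles". It concludes that putting people in the right condition will be easy, and states no threshold or rule.

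The Hypothesis 2 analysis lists as predictors the group (or continuous blood THC), time, and their product. It supports causal reading of the group comparison by appeal to random assignment.

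**The concern.** The design section and the eligibility section do not describe the same people. For edibles the exposure is the participant's own habit, so how much edible habit a participant has is part of what defines the exposure. The dose groups are not randomised. Anything related both to the dose a person chooses and to how that person responds can therefore enter the low-versus-high comparison. Experience with edibles is one plausible such factor, and the criteria leave it free to range from a single past occasion to frequent use.

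At stake are the interpretation of any edible dose-harm gradient and the description of the population to which it applies.

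**Working it through.** **1. The plan's own figure.** *Power Analysis* gives three groups, four assessments, ICC 0.6, two-tailed alpha 0.05, N = 99 and f = 0.12. For a within-between interaction, lambda = f² × N × m / (1 − ICC) = 0.0144 × 99 × 4 / 0.4 = 14.26 on 6 and 288 degrees of freedom, which gives power 0.811. The stated 0.80 is reproduced. The point here does not depend on this calculation, which serves only as a scale in step 5.

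**2. Two hypothetical callers against the criteria.** Assume each meets every item unrelated to form.

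| Criterion | Caller A: flower four times last month, one edible ever, for the edible group | Caller B: wax only, four times last month, for the flower group |
|---|---|---|
| Item 2, edible experience | met | not applicable |
| Item 3, four uses | met by flower | met by wax |
| Item 4, THC and CBD percentage | met if the flower strain qualifies | met if the product qualifies |
| Regular use of the study form | no such item | no such item |

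Both pass the criteria as written. Neither fits the population in the design section.

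**3. Does another provision close the gap?** Item 4 is on a percentage scale, so it sets neither a usual edible dose in mg nor a frequency for any form. The statement in *About the Subjects* points toward placement by habitual form, but it is an expectation rather than a criterion. The Timeline Follow-Back, given at Sessions 1 and 2, records frequency, amount and method of administration. The information is therefore collected, but no criterion uses it and it is not among the stated Hypothesis 2 predictors.

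**4. Where it matters.** *Marijuana Administration at Home* urn-randomises the instruction to buy Strain A, B or C. Within flower, caller B is as likely to fall in one potency group as another, so the gap affects generalisability and not the strain contrast. The edible groups are self-chosen, so a person like caller A can be more common in one dose group than another.

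**5. Size.** Let p be the share of a dose group without regular edible use. Let δ be how much more such people respond, in SD units, than regular edible users at the same dose. Then the bias in the high-minus-low contrast is (p_high − p_low) × δ. The documents give none of these quantities. The values below are assumptions.

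| Difference in shares (absolute) | δ = 0.3 | δ = 0.5 | δ = 0.8 |
|---|---|---|---|
| 0.20 | 0.06 SD | 0.10 SD | 0.16 SD |
| 0.40 | 0.12 SD | 0.20 SD | 0.32 SD |

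For scale, suppose a group effect with scores −d, 0, d that is present only at Sessions 3 and 4. The interaction cell effects are then plus or minus half the group score, with SD √((2/3) × d² × (1/4)) = d/√6. Setting this to 0.12 gives d = 0.294 and a low-versus-high difference of 0.588 SD. The table then runs from 0.06/0.588 = 10% to 0.32/0.588 = 54% of that difference. The 0.588 SD corresponds to the smallest effect the plan says it can detect, not to an expected effect.

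The sign is open. If non-regular edible users cluster at low doses and respond more, the contrast shrinks. If they are heavy users of another form who choose high doses, or who respond less, it can move the other way. If their shares are equal across dose groups, the bias is zero.

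**The case against.** The strongest defence is that item 2 is a minimum condition and not the rule that puts someone in the edible group, since *About the Subjects* implies placement by habitual form. That is a fair reading, and it rules out one tempting inference: that the people enrolled are not the population the design describes. The text shows only that others are not excluded. It does not remove the gap, because no rule or threshold for placement is given.

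A reader might also infer that the loose criterion is what confounds dose with tolerance. It is not. Self-chosen dosing would do so even among strictly regular edible users, and tightening the criterion would leave that in place. The criterion adds an avoidable source.

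A third inference is that people with little edible experience choose low doses and react more strongly, so that the dose-harm contrast is diluted or reversed. Nothing in the documents supports this. Everyone enrolled has used cannabis at least four times in the past month, and someone who uses much flower but few edibles may be tolerant to THC.

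It would also go too far to say that the instruction to follow one's usual habit is meaningless for an occasional edible user, who may still have a usual amount.

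Finally, the listed predictors need not be exhaustive, and a statistical analysis plan not shown here could add covariates. That limits any claim that the full plan has no adjustment. It does not settle the disagreement over eligibility or the appeal to random assignment, both of which are in the protocol. The fallback to continuous blood THC deals with differences in dose and absorption, but not with differences in experience.

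**Conclusion.** The mismatch is real. The design section describes regular users of each form, while the criteria used for screening require regular use of neither. For edibles, this adds variation in form-specific experience to a non-randomised dose comparison that is already open to confounding. For flower, it affects only whom the results describe. The size and direction of any bias cannot be derived from the documents, and the 0.06 to 0.32 SD range rests wholly on assumed shares and response differences, with either sign possible. The conclusion rests on the wording of the sections and on the edible doses being self-chosen. It is worth correcting because the remedy is cheap and the data are already planned.

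**What to change.** 1. Reconcile *Overview and Design of Study 1*, *About the Subjects* and inclusion items 2 and 3. Either require the past-month frequency to be met in the form the participant will use in the study, or redefine the populations in the overview to match the criteria. State the rule that places a person in the flower or the edible group.
2. In the edible models, add baseline form-specific use from the Session 1 Timeline Follow-Back (frequency and amount by method of administration), with its interaction with time. The primary test is group by time, and a covariate main effect alone shifts a participant equally at all sessions, so it does little to adjust that interaction.
3. State that the random-assignment rationale under Hypothesis 2 does not apply to the edible groups, and describe those comparisons as observational.

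**Cost.** This needs a short amendment and no new data collection. Somewhat fewer callers may qualify for the edible group if the frequency rule becomes form-specific. With time as four categories, each covariate uses one between-subject degree of freedom and three within-subject ones, so two covariates use 6 of the 288 in the plan's own design. Adjustment reduces confounding from self-chosen dose but does not remove it.
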